**Visit 0: Previously scheduled office visit:**

- Provider reviews study with patient, confirms that inclusion/exclusion criteria are met, and obtains informed consent.
- a. Note: If any labs or ECG are required, results will be reviewed by the provider and the patient will resume study activities at their next scheduled visit.
- Provider documents characteristics of wound via PUSH Tool 3.0, obtains plantar pressure profile reading, and captures clinical photos.
- Provider verifies and documents concomitant medications in the patient's chart.
- Provider visualizes and evaluates any additional wounds that are present and records characteristics in the patient's chart.
- Patient is randomized to receive either oral immunonutrition supplementation with standard of care or standard of care alone.
- Patient is provided oral immunonutrition supplements and compliance log, if appropriate.

**Phone Call 1: (1 Week Call, first call after completing 7 days of oral immunonutrition):**

- Patient completes questionnaire over phone with research coordinator (VAS, experienced symptoms since enrollment, review of supplement compliance).

**Visit 1: 2 Week Follow-up (First visit after completing 14 days of oral immunonutrition):**

- Provider documents characteristics of wound via PUSH Tool 3.0, captures clinical photos, obtains interval history, performs interval physical exam, and verifies and documents concomitant medications in the patient's chart.
- Provider visualizes and evaluates any additional wounds that are present and records characteristics in the patient's chart.
- Patient completes questionnaire in clinic (VAS, experienced symptoms since enrollment, review of supplement compliance).

**Phone Call 2: (3 Week Call, second call after completing 21 days of oral Immunonutrition):**

- Patient completes questionnaire over phone with research coordinator (VAS, experienced symptoms since enrollment, review of supplement compliance).

**Visit 2: 4 Week Follow-up (Second visit after completing 28 days of oral immunonutrition):**

- Provider documents characteristics of wound via PUSH Tool 3.0, captures clinical photos, obtains interval history, performs interval physical exam, and verifies and documents concomitant medications.
- Provider visualizes and evaluates any additional wounds that are present and records characteristics in the patient's chart.
- Patient completes questionnaire in clinic (VAS, experienced symptoms since enrollment, review of supplement compliance).

**Phone Call 3: (5 Week Call, third call after completing 36 days of oral immunonutrition):**

- Patient completes questionnaire over phone with research coordinator (VAS, experienced symptoms since enrollment, review of supplement compliance).

**Visit 3: 6 Week Follow-up/Completion Visit (Third visit after completing 42 days of oral immunonutrition):**

- Provider documents characteristics of wound via PUSH Tool 3.0, obtains plantar pressure profile reading, captures clinical photos, obtains interval history, performs interval physical exam, and verifies and documents concomitant medications.
- Provider visualizes and evaluates any additional wounds that are present and records characteristics in the patient's chart.
- Patient completes questionnaire in clinic (VAS, experienced symptoms since enrollment, review of supplement compliance).
- Patient completes satisfaction survey detailing their experience with supplementation (if applicable).
- Patient returns compliance log (if applicable).
- Provider orders CMP and lipid panel labs to be drawn at this timepoint or within 3 months of study completion.

**Phone Call 4: (Final Safety Follow-up, 6-8 weeks after completing oral immunonutrition, if randomized to treatment group):**

- Provider reviews and records adverse events experienced after supplement discontinuation and visualizes wound.

**g. Data and Specimen Banking**

Data collected from this study will be stored in the Prisma Health REDCap. Images will be stored on a password-protected network. No specimens will be collected as part of this research study. Only authorized research members of this study can access this information.

#### **h. Statistical Analysis**

Summary statistics will be used to summarize measurements and assessed for unadjusted differences across treatment condition. Student's t-tests will be used for continuous measures, exact binomial tests for dichotomous measures, and chi-square tests for categorical measures.

The main outcome of interest is the proportion of wound closed at the end of 6 weeks which we will model in a generalized linear models framework

$$E[g(y_i)] = \beta_0 + Trt_i\beta_1 + Z_i\gamma$$

where  $y_i$  is the outcome measure of interest of the  $i$ th participant,  $Trt_i$  is an indicator variable of whether the participant was assigned to the treatment condition,  $Z_i$  is a vector of covariates for which we will adjust the model (i.e., initial wound size, diabetes etiology, sex, race, and age), and  $\gamma$  is a vector of regression parameters. We have written the outcome in terms of a link function ( $y_i$ ) to emphasize that we will estimate a linear regression model (identity function) as well as a zero-one augmented beta regression model for which we will choose from among several link functions (logit, log, log-log, and complementary log-log). Anticipating that we will have outcomes of exactly 0% or 100% reduction of the wound size, we will model the transformed outcome

$$y_i^* = \frac{99y + 0.5}{100}$$

Our focus is on the null hypothesis  $H_0: \beta_1 = 0$ . We will evaluate this null hypothesis using a Wald test of the parameter based on an appropriate variance estimate – chosen from model-based, sandwich, or sandwich based on an evaluation of the implied dispersion properties of the model-based variance estimator.

Other secondary outcome variables to be modeled include the time to complete healing (Cox proportional hazards regression), rate of closure (Cox proportional hazards regression), presence of infection (binary regression), and need for surgery (binary regression). Cox proportional hazards models will be used to interpret the relative hazards between treatment conditions. The proportional hazards assumption will be checked using Schoenfeld residuals and accelerated failure time (parametric) regression models will also be evaluated. Binary outcomes will be modeled using various link functions (logit and log). Exponentiated coefficients for logit-link models will be interpreted as odds ratios, and exponentiated coefficients from log-link models will be interpreted as risk ratios. Binary outcomes may be relatively rare, and so we will also

estimated binary models using exact statistics. In addition, we will investigate bias through estimation of bias-corrected models.

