## 2) Objectives / Research Aims

Chronic, non-healing foot ulcers are a common complication of diabetes that can threaten loss of limbs, shorten life expectancy, and require resource-intensive treatment. Patients who exhibit these late effects of diabetes are often medically complex and have not only a shortened life expectancy but also a lower quality of life than their non-ulcer peers. Despite the prevalence of obesity in these patients, many exhibit metabolic signs of malnutrition, malabsorption, or both. Even when direct treatment for the ulcer is ideal, if the patient does not have the metabolic building blocks or the correct macronutrient healing environment, then treatment will be futile.

To this end, we believe focused immunonutrition supplementation consisting of L-Arginine, Omega-3 fatty acids, and Vitamin C combined with quality wound care will lead to an improvement in treatment success, satisfaction, patient reported outcome measures, and limb salvage.

**Specific Aim 1:** To compare the healing process of diabetic patients with chronic, non-healing, lower-extremity wounds receiving oral immunonutrition supplementation to patients receiving traditional care.

- a. This will be addressed by performing a prospective, randomized pilot study including 30 diabetic patients with chronic lower extremity wounds, Wagner stages 1-2. Fifteen patients will receive oral immunonutrition supplementation (2 grams omega-3 fatty acids + 500 mg vitamin C + 4.5 grams L-arginine per day) in addition to current standard of care and 15 patients will receive the current standard of care only. Study participation will continue for 6 weeks.
- b. Effect of wound healing will be assessed utilizing the Pressure Ulcer Scale for Healing (PUSH) Tool 3.0 which scores ulcers based on size ( $\text{cm}^2$ ), exudate amount, and tissue type present. Plantar pressure profiles will be recorded using a Tekscan Pressure Mat and plantar weight-bearing foot images will be recorded. Additionally, patient charts will be monitored over the course of the study to identify rate of infection, surgical intervention, and amputation and for one year following completion of the study to assess ulcer recurrence rates.

**Specific Aim 2:** To assess compliance and patient satisfaction with an oral immunonutrition supplementation regimen in diabetic patients with chronic, non-healing, lower-extremity wounds.

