**f. Procedures Involved**

1. A research coordinator within the Prisma Health Orthopedics department will review weekly clinic schedules of participating providers at the Wound Healing Center to flag patients who may qualify for the study and are scheduled for an upcoming office visit. The provider scheduled to see the patient will be informed of potential subjects for inclusion.
2. At the office visit, the provider seeing the patient will inform the patient of the research study, screen to ensure eligibility criteria are met, and, if appropriate, consent the patient to participate in the study. The study will be thoroughly explained to the subject and all questions/concerns will be addressed. Research team members will be available to assist if the patient agrees to participate with the provider.

- a. Note: If the patient has not had an ECG (within 3 months of study enrollment), a lipid panel (within 3 months of study enrollment), a CMP (within 3 months of study enrollment, an INR/PT (within 3 months of study enrollment), and/or an A1c lab (within 6 months of study enrollment) these will be performed to confirm normal parameters prior to continuation of study activities. If any labs or ECG are required, results will be reviewed by the provider and the patient will resume study activities at their next scheduled visit.
3. The provider will document wound characteristics via the PUSH Tool 3.0 (Appendix 2). Plantar pressure profile readings will be obtained using a Tekscan Pressure Mat and clinical plantar weight-bearing images will be captured. The provider will verify and document concomitant medications in the patient's chart. The provider will visualize and evaluate any additional wounds that are present and record characteristics in the patient's chart.
4. The patient will be randomized to the control group or treatment group via a pre-defined randomization table in which subject IDs are already assigned as belonging to either group.

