  - a. If randomized to the control group (SOC only), patients will receive standard of care defined as sharps debridement, appropriate dressing, and offloading. If randomized to the treatment group (SOC + Immunonutrition), subjects will receive standard of care defined as sharps debridement, appropriate dressing, and offloading in addition to a 6-week supply of Omega-3 fatty acids (soft gel form, 2 pills per day, total of 1.68 grams) and L-Arginine/Vitamin C (powder form, to be mixed with 8 oz liquid, 1 scoop once daily, total of 4.5 grams L-arginine and 500 mg vitamin C). Subjects will also be provided a compliance log with detailed instructions for taking and tracking supplements.
5. Patients will be scheduled for biweekly wound checks with their provider (weeks 2, 4, 6). Wound characteristics will be documented at each follow up visit using the PUSH Tool 3.0, images of the wound will be obtained, and an interval history and physical exam will be documented. The provider will verify and document concomitant medications in the patient's chart. The provider will visualize and evaluate any additional wounds that are present (new or present at time of enrollment) and record characteristics in the patient's chart. Patients will complete a questionnaire detailing their pain level (VAS), symptoms experienced during the treatment phase, and any unscheduled visits to emergency departments/urgent care centers. This will be completed via a paper survey in clinic during their office visit (Appendix 4). On weeks where an office visit is not scheduled (weeks 1, 3, 5), a research coordinator will call the patient and collect survey responses (Appendix 3).
6. At the final office visit (week 6), plantar pressure profiles will be recorded via the Tekscan Pressure Mat, and clinical plantar weight-bearing images will be captured. Patients randomized to receive the oral immunonutrition supplementation will complete an additional survey detailing their satisfaction with the treatment plan and any additional thoughts they would like to share (Appendix 5) and return the completed compliance log

(Appendix 6). Patients in the treatment arm will have CMP and lipid panel labs drawn at this timepoint or within 3 months of study completion.

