### **Biweekly Office Visits**

- Document characteristics of wound via PUSH Tool 3.0, obtain pressure profile reading (visits 0 and week 6), capture clinical photos, obtain interval history, perform interval physical exam, verify and document concomitant medications, visualize and record characteristics of additional wounds present.
- Patient completes questionnaire (VAS, experienced symptoms since enrollment, review of supplement compliance (if applicable))

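### Plantar pressure is read at Visit 0 and week 6, but section 6h plans no baseline-adjusted comparison of it and does not say whether the default t-test uses the week-6 value or the change

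*Combined protocol and SAP*

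**What the plan says.** Specific Aim 1b (section 2), in its paragraph on how wound healing will be assessed, states: "Plantar pressure profiles will be recorded using a Tekscan Pressure Mat". Section 6f takes the first reading in step 3, before randomisation in step 4: "Plantar pressure profile readings will be obtained using a Tekscan Pressure Mat and clinical plantar weight-bearing images will be captured". It takes the second at the end of treatment: "At the final office visit (week 6), plantar pressure profiles will be recorded via the Tekscan Pressure Mat". Appendix 1 confirms the two time points: "obtain pressure profile reading (visits 0 and week 6". Neither reading is restricted to one arm. Section 6i lists the readings among the key data points.

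Section 6e does not include plantar pressure among its primary, secondary or tertiary outcomes.

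Section 6h does not mention plantar pressure. Its opening rule is general: "Summary statistics will be used to summarize measurements and assessed for unadjusted differences across treatment condition", with Student's t-tests for continuous measures. The covariate-adjusted model that follows is for the proportion of wound closed. Its covariates are starting wound size, type of diabetes, sex, race and age. The other outcomes given a model are healing time, closure rate, infection and surgery.

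**The concern.** The trial collects a pre-randomisation value of a continuous measure in every patient, yet plans no analysis that adjusts for it. For the wound outcome, 6h does adjust for the starting value (initial wound size), so the principle is already accepted elsewhere in the same section.

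With 15 per arm, an unadjusted comparison carries between-patient variation that the Visit 0 reading could partly remove. A chance difference between arms at Visit 0 also passes in part into the estimate. Because 6h does not say which quantity is tested, the week-6 value or the change could be chosen after the data are seen, and the two can give different answers.

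**Working it through.** The plan has no figure to reproduce. Section 6c gives 30 patients, 15 per arm, as a pilot size, without a significance level, power, target difference or SD.

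**Inputs**
- From the documents: n = 15 per arm; one reading before randomisation and one at week 6.
- Assumed: two-sided 5%; true difference 0.8 SD; equal SD at both times; baseline to week-6 correlation r from 0 to 0.9; complete data.

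**Formulas**, in units of the plantar pressure SD. The standard error is SE = √(2v/15), where v is the variance factor:
- t-test on week 6: v = 1, 28 df
- t-test on change: v = 2(1 − r), 28 df
- ANCOVA on the Visit 0 value: v = (1 − r²)(1 + 1/26), 27 df. The second factor is the cost of estimating the slope.

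Example at r = 0.5. Week 6: √(2/15) = 0.365. Change: v = 2 × 0.5 = 1, so SE is again 0.365. ANCOVA: v = 0.75 × 1.038 = 0.779, so SE = √(2 × 0.779/15) = 0.322.

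Power is from the noncentral t distribution with noncentrality 0.8/SE:

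| r | Week-6 t-test | Change t-test | ANCOVA |
|---|---|---|---|
| 0 | 56.2% | 32.2% | 54.5% |
| 0.3 | 56.2% | 43.2% | 58.4% |
| 0.5 | 56.2% | 56.2% | 66.8% |
| 0.7 | 56.2% | 77.9% | 82.7% |
| 0.9 | 56.2% | 99.7% | 99.7% |

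A simulation of 20,000 trials at each of r = 0.3, 0.5, 0.7 and 0.9 agreed within one percentage point.

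The difference detectable with 80% power is 1.06 SD for the week-6 t-test at every r. At r = 0.3 / 0.5 / 0.7 it is 1.25 / 1.06 / 0.82 SD for the change score and 1.03 / 0.94 / 0.77 SD for ANCOVA.

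**Chance imbalance at Visit 0.** The difference in baseline means has SD √(2/15) = 0.365. A gap above 0.5 SD in either direction has probability 2(1 − Φ(0.5/0.365)) = 0.17. A gap of 0.5 SD moves the week-6 estimate by 0.5r, which is 0.15 / 0.25 / 0.35 SD at r = 0.3 / 0.5 / 0.7. It moves the change estimate by 0.5(r − 1), which is −0.35 / −0.25 / −0.15 SD. ANCOVA removes this shift if the relation to baseline is linear.

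**The case against.** The strongest reply is that no stated inference depends on this comparison. Plantar pressure is not an outcome in 6e, Aim 1b says only that it will be recorded, and the hypothesis in section 2 concerns treatment success, satisfaction, patient-reported outcomes and limb salvage. Nothing in the plan predicts an effect of the supplement on pressure, so the 0.8 SD difference is only illustrative. This stands, and it limits the importance of the point.

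A second reply is that the variable must come first. No summary of the pressure profile is defined, nor a foot or region, and eligibility requires a lower extremity wound, not specifically a plantar one. This also stands, and the fix has to begin there.

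Three stronger readings are tempting, and the documents do not support them:
- A reader might infer that 6h sets a t-test for plantar pressure. It does not name the measure; the t-test applies only by default, through the general rule.
- A reader might infer that the Visit 0 reading is ignored, and set 56% power against 83% at r = 0.7. That holds only if the week-6 value is tested. A t-test on change fits 6h equally well and uses the baseline; the contrast is then 78% against 83%.
- A reader might infer that chance imbalance biases the result or raises the false-positive rate. Under randomisation the unadjusted comparison is unbiased on average and keeps its type I error, and its standard error already allows for such imbalance. The shift belongs to the single trial in which the imbalance occurs.

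**Conclusion.** The point holds as a minor improvement. Both readings are collected, no baseline-adjusted analysis is planned, and the default t-test leaves its variable open. Under the stated assumptions, ANCOVA gains about 2, 11 and 27 percentage points of power over a week-6 t-test at r = 0.3, 0.5 and 0.7, and about 15, 11 and 5 points over a change-score t-test. Whichever t-test was meant, ANCOVA does at least about as well: its only loss is 1.7 points (56.2% to 54.5%) against the week-6 test at r = 0.

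The actual gain cannot be derived from the documents, because they give no correlation or SD for plantar pressure. It could be negligible or large. It does not touch the trial's primary, secondary or tertiary outcomes.

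**What to change.** In 6h, name one plantar pressure summary variable and the foot on which it is read. State that arms will be compared by a linear model of the week-6 value on arm and the Visit 0 value of the same variable, in place of the unadjusted t-test. Report the adjusted difference with its 95% confidence interval, and label the analysis exploratory. Naming a single variable also avoids undeclared multiple comparisons across summaries of the profile.

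The cost is a sentence or two in 6h, a decision on the variable before the data are examined, and one degree of freedom (27 instead of 28). No new visits or measurements are needed.

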**e. Study Endpoints**

Primary Outcome: Complete wound closure of a chronic, non-healing wound at 6 weeks.

- a. Complete wound closure will be defined as skin reepithelialization without drainage or dressing requirements confirmed at two consecutive study visits 2 weeks apart. Incidence of complete wound closure in the control group will be compared to that of the treatment group.

Secondary Outcome: Rate of wound closure over 6-week study period.

- a. PUSH Tool 3.0 scores and clinical photos will be compared between the control group and treatment group to evaluate the rate of wound closure over the course of the 6-week study period.

Tertiary Outcome: Compliance and patient satisfaction with immunonutrition supplementation regimen.

- a. Patient satisfaction surveys and compliance logs will be evaluated to assess feasibility of implementing an immunonutrition regimen into standard wound care.

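### The exact binomial test named for unadjusted yes/no comparisons is a one-sample test; a two-sample exact test should be named and tied to the complete-closure endpoint

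*Combined protocol and SAP*

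**What the plan says.** Section 6h (Statistical Analysis) opens with a general paragraph. Measurements are summarised and "assessed for unadjusted differences across treatment condition", and the tests are then assigned by type of variable: "Student's t-tests will be used for continuous measures, exact binomial tests for dichotomous measures, and chi-square tests for categorical measures". No null proportion, two-sample version, alpha or sidedness is given.

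Section 6e (Study Endpoints) defines a yes/no primary endpoint: "Primary Outcome: Complete wound closure of a chronic, non-healing wound at 6 weeks". The comparison is between two arms: "Incidence of complete wound closure in the control group will be compared to that of the treatment group". Section 6c sets 15 patients per arm.

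The rest of 6h deals with other outcomes. It states "The main outcome of interest is the proportion of wound closed at the end of 6 weeks", models that fraction by linear and beta regression, and says of the treatment coefficient "We will evaluate this null hypothesis using a Wald test of the parameter". Among the secondary outcomes it lists time to complete healing and rate of closure (Cox regression), then "presence of infection (binary regression), and need for surgery (binary regression"). It adds "Binary outcomes will be modeled using various link functions (logit and log"), with exact and bias-corrected versions. Complete closure at 6 weeks, as a yes/no outcome, is not in that list.

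**The concern.** The sentence is about differences between two randomised arms, but the test it names has only one sample. It asks whether an observed count fits a proportion known in advance. In this trial both proportions are estimated, each from 15 patients, so the test cannot be run without a choice that the plan does not make. Two literal choices are available:

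- **Fixed control rate.** The observed control rate is treated as a known constant and the treatment arm is tested against it. This ignores the sampling error of the control arm and makes p-values too small.
- **Share of closures.** All closures are pooled and the treatment arm's share is tested against one half. This ignores the patients who did not close and makes p-values too large.

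The declared primary endpoint is yes/no, and no other test in 6h is explicitly directed at it. What is at stake is therefore the unadjusted p-value for complete closure, and the freedom to choose between tests that disagree after the data are seen.

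**Working it through.** **Inputs from the plan.** 15 patients per arm (6c); a yes/no endpoint compared between arms (6e); exact binomial test for yes/no measures (6h). The plan gives no alpha, sidedness, power or expected closure rate, so it has no figure to reproduce.

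**Assumptions.** Two-sided 5%; true closure rates of 10% to 50%, equal in both arms for type I error; 20% v 60% for power.

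**Method.** With c control closures and t treatment closures, each from 0 to 15, there are 16 × 16 = 256 possible results. Each has probability Bin(c; 15, p_C) × Bin(t; 15, p_T). The rejection rate is the sum of these probabilities over all results with p ≤ 0.05. The tests are:

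- *Fixed control rate*: exact binomial test of t out of 15 against c/15.
- *Share*: exact binomial test of t out of (c + t) against 0.5.
- *Fisher* and *Boschloo*: two-sample exact tests, with the arm sizes as the fixed margins for Boschloo.

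**Type I error**

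| True closure rate | Fixed control rate | Same, 0/15 and 15/15 control tables never rejected | Share | Fisher |
|---|---|---|---|---|
| 10% | 20.2% | 3.9% | 0.1% | 0.6% |
| 20% | 17.6% | 14.3% | 0.6% | 1.7% |
| 30% | 17.5% | 17.0% | 0.6% | 1.7% |
| 40% | 14.7% | 14.6% | 0.4% | 1.6% |
| 50% | 12.9% | 12.9% | 0.2% | 1.7% |

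The two fixed-rate columns differ because a control arm with no closures sets the null value at exactly zero, and then a single treatment closure rejects. At a 10% rate the chance of 0/15 in the control arm is 0.9^15 = 20.6%, so this convention decides the result there. At 20% it is 0.8^15 = 3.5%, and at 30% or more it hardly matters. Boschloo stays below 5%, at 4.0-4.3% for rates of 20-30%.

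**Power at 20% v 60%.** Share 26%, Fisher 45%, Boschloo 60%. The fixed-rate test is left out because its type I error is not controlled.

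**One data set, four answers.** Suppose 7/15 close on treatment and 3/15 on control.

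- Fixed control rate: the null is 3/15 = 0.2. P(X ≥ 7 | 15, 0.2) = 0.0181. No result in the lower tail is as unlikely as 7 (even X = 0 has probability 0.035, against 0.014 for X = 7), so the two-sided p = 0.018.
- Share: 7 of 10 closures. p = 2 × P(X ≥ 7 | 10, 0.5) = 2 × 176/1024 = 0.344.
- Fisher: p = 0.245.
- Boschloo: p = 0.142.

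The first is significant at 5%; the other three are not.

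**The case against.** The strongest reply is that the phrase may be loose wording for a two-sample exact test of binomial proportions, such as Fisher's. On that reading the p-value is valid and only the name needs correcting. The plan supplies no null value, and the two literal readings err in opposite directions, so the documents commit to neither. This stands, and it makes the harm conditional. It does not remove the point: the test should be fixed before the data are seen, and even the valid candidates differ (0.245 and 0.142 above).

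Three stronger readings are tempting but not supported:

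- *The plan assigns this test to the primary endpoint.* It does not do so by name. The sentence is a general rule by variable type, and the main modelling paragraph of 6h tests a different, continuous outcome with a Wald test. The link is an inference from closure in 6e being yes/no. The mismatch between the 6e endpoint and the 6h main outcome is a separate issue.
- *All yes/no comparisons depend on this test.* Infection and need for surgery also have two-arm binary regression with exact versions. The general sentence on links for binary outcomes could be stretched to cover closure, but it follows a list of secondary outcomes in which closure at 6 weeks does not appear.
- *The primary p-value will be invalid, with a false-positive rate of 20%.* That figure arises only at a 10% closure rate with zero-closure control arms allowed to reject. If such tables are never rejected, it is 3.9%.

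The same sentence's chi-square tests might also be questioned at this sample size, but the plan names no categorical outcome, so that concern cannot be sized.

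That this is a 30-patient pilot limits how much any test can show, but 6h still plans hypothesis tests, and a control arm of 15 is where ignoring its sampling error matters.

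**Conclusion.** The concern holds as a defect in the named method. An exact binomial test, as usually understood, is not a valid comparison of two arms of 15, and it is the only explicit test in the plan that reaches complete closure as defined in 6e.

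The size depends on how the analyst would carry it out. Treating the observed control rate as fixed raises the type I error to about 13-18% at closure rates of 20-50% (13-17% if 0/15 and 15/15 control tables are never rejected). Testing the share of closures holds it at 0.6% or less, but at 20% v 60% it gives up 19 points of power against Fisher (45 − 26) and 34 against Boschloo (60 − 26). If a two-sample exact test was meant, there is no numerical error, only a wrong name. All these figures rest on an assumed two-sided 5% level and assumed closure rates.

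**What to change.** In section 6h, replace exact binomial tests with one named two-sample exact test, and state its alpha and sidedness. Boschloo's test is a reasonable choice because it had more power than Fisher here while keeping type I error below 5%; Fisher or Barnard would also cure the defect. State that this test is the unadjusted analysis of complete closure at 6 weeks as defined in 6e, and report the risk difference between arms with a 95% interval.

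The cost is a change of wording and a little analysis work. The methods are in standard software, and no new data or visits are needed.
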